Therefore, we hypothesize that the use of CMC in artificial tears may affect the eye microbiome and influence ocular diseases. Similar studies on microbiome composition used bacterial ribosomal RNA sequencing and statistical analysis with existing R packages such as phyloseg and DADA2. A UF investigator, [name], recently conducted a microbiome study entitled "The gut microbiome of COVID-19 recovered patients returns to uninfected status in a minority dominated United States cohort" at the University of Florida in 2021. For these reasons, we are conducting a similar study on the use of artificial tears containing CMC compared to control artificial tears without CMC. Results of this study will lead to a better understanding of the risks and benefits associated with CMC artificial tears for eye lubrication and dry eye disease.

5. Specific Aims:

We aim to examine whether carboxymethylcellulose in artificial tears changes the eye microbiome and identify which bacterial genera are enriched.

6. Research Plan:

Before Study Enrollment

- 1. Staff creates Excel key and labels with identifiers
- 2. Screen clinic schedule for inclusion and exclusion criteria
- 3. Study staff assigns and labels cardboard boxes with numerical identifiers, then attaches spare labels
- 4. Principal investigator fills boxes with control or CMC artificial tears, consent copies, and patient instructions, then seals the boxes with tape
- 5. Store boxes on-site for staff

Initial Study Schedule

- 1. Participant checks into clinic and receives clinical workup
- 2. [name] approaches, recruits, and enrolls patient.
- 3. Staff ensures patient meets criteria at time of visit
- 4. Participant signs consent form
- 5. Staff gives a random box to the participant and attaches box label to informed consent form
- 6. Participant completes survey 1
- 7. Licensed staff collect 1st swab
- 8. Participant has a normal clinic visit and is scheduled to return

Second Study Schedule

- 1. Participant checks into clinic and receives clinic workup 1 week after initial visit
- 2. If participant does not have box labels, the informed consent form label is consulted to associate surveys and data
- 3. Participant completes survey 2
- 4. Staff ensures that both surveys are completed and recorded
- 5. Licensed staff collects 2nd swab
- 6. Participant completes a normal clinic visit and has thereafter completed the study

Tasks Throughout Study Duration

- 1. Freeze and transport samples to lab for temporary storage
- 2. Lyse, amplify, and sequence samples, then store sequences 5. Relevant chart review and record data for each participant
- 3. Analyze sequences with R statistical packages
- 4. Monitor for harms in clinic at visit and treat accordingly
- 6. Statistical analysis of sampled microbiomes by R packages

- Recruitment: During the spring of 2022, 80 patients of the UF Oaks Eye Clinic who meet inclusion criteria will be identified by study staff prior to their visit by chart review using the Epic electronic medical record and clinic scheduler on a secure encrypted UF computer. Up to 20 participants are expected to drop out over the course of this study. When patients have completed their clinical workup, [name] will approach patients without exclusion criteria to ascertain willingness/interest in the study, then recruit them. Study staff will give willing participants the appropriate informed consent form and counsel participants for consent to enroll in a private examination room. Completed consent forms will labelled with the participant's randomly selected numerical identifier as described below and stored securely in the UF Oaks Eye Clinic Office.
- Participant Criteria: This study includes adults above age 18 of either sex who can self-administer artificial tears and are scheduled to return for clinical follow-up in 1 week. This study excludes individuals with active eye infections, have prosthetic eyes, are immunocompromised, or are diagnosed with autoimmune diseases or malignant neoplasms about the eye. Individuals who take immunomodulatory therapy, steroids, antibiotics, medicated eyedrops, or are already using CMC artificial tears within 1 week of the study will also be excluded. These criteria maximize the number of self-consenting participants while minimizing participants whose compliance, conditions, or medications may change the eye microbiome.
- Research Intervention: Participants will be given either artificial tears without CMC (control) or commercial artificial tears containing CMC (treatment) and told that they may have received either CMC or a placebo. Both are FDA-approved for over-the-counter use and for treatment of dry eye. Both interventions are standard therapies for dry eye disease. Prospective participants have the option to not enroll in the study, and the alternative is to complete a normal clinic visit. Individuals for whom artificial tears do not constitute standard therapy are excluded from this study.
- Assignment: This study design will include an experimental control, random assignment, and double blinding of staff and participants. The principal investigator will create a securely saved Excel spreadsheet with unique randomly generated numerical identifiers keyed to either the control group receiving artificial tears without CMC or the treatment group receiving CMC artificial tears. The principal investigator will then create plain cardboard boxes with the identifier on removable adhesive labels. Boxes will contain a copy of the informed consent form, participant instructions, and 21 plastic vials of either artificial tears without CMC or CMC artificial tears as assigned on the identifier spreadsheet. Patients will be blinded to their assigned intervention group. Study staff other than the principal investigator, who are blinded to box contents, will give participants a randomly selected box and an electronic survey (PDF) on an encrypted clinic computer in their private examination room. Labels will be placed on consent forms and identifiers will replace personal identifying information on electronic surveys.
- **Data Collection:** Electronic surveys will contain the Ocular Surface Disease Index and a box for entry of the patient's unique identifier. After completion of the survey, licensed physicians serving as study staff will swab the participant's right and left eye conjunctiva with a single cotton tip applicator, seal the applicator in a sample

- tube, attach a label, and freeze it for storage in dry ice. The participant will complete a normal clinical schedule afterwards and will be scheduled to return in 1 week. Upon 1 week follow-up, participants will be swabbed again and complete a second survey. The second survey will be identical to the first survey but contain an additional question quantifying eye drop use to measure compliance. Patients will complete a normal clinical schedule afterwards. Study staff will correlate identifiers to patients using the informed consent forms and record ophthalmic history, ophthalmic medications, age, gender, tobacco usage, diabetes status, and race by chart review during this study.
- Sample Processing and Data Analysis: Samples will be frozen at -80 degrees Celsius and transported to a BSL-2 lab at UF for processing. During processing, samples will be lysed, amplified, and sequenced for bacterial 16S RNA using protocol supplied by Illumina MiSeq. Swabs and container tubes will be destroyed after sequencing. The sequenced bacterial microbiome of each sample will then be trimmed, error-corrected, and classified using the DADA2 R package as described in the article described above (Newsome 2021). After all samples are sequenced, microbiomes will be grouped by principal coordinate analysis using the phyloseq R package. Shannon's diversity indices will be calculated using the phyloseq R package. Differences in alpha diversity before and after treatment will be tested by PERMANOVA using the vegan R package, and differences in beta diversity will be tested by ANOVA using the nlme R package.
- Data Security: The original consent forms with unique identifier stickers will be kept securely in a folder and stored in a locked office within the UF Oaks Eye Clinic. Surveys will be accomplished on a pdf and do not contain any participant identification aside from the study-assigned numerical identifier. All other documents and data files will be deidentified and stored on an encrypted computer within the UF IT environment. Only medical students, resident physicians, and attending physicians serving as study staff will access participant medical records on the Epic EMR using a secure encrypted computer or smartphone. This study will not have a Data Safety Monitoring Board. [name] will serve as oversight for this research project and will meet weekly with study staff to monitor study conduct and patient safety.

7. Possible Discomforts and Risks:

Enrolled study participants may more commonly encounter mild eye discomfort during conjunctival swabs, anxiety regarding assignment to a treatment group, short delays in clinic flow (1-2 minutes), and inconvenience of completing surveys during the study.

Rare discomforts or risks may include breach of protected patient data, eye pain, dry eye, eye infection, and eye trauma including corneal abrasions and conjunctival hemorrhage because of methods used in this study. Participants will not be charged for any time, medication, or procedure used in this study.

To minimize anxiety and medical risks, patients will receive counseling and treatment interventions in the setting of the UF Oaks Eye Ophthalmology Clinic by a licensed attending ophthalmologist or an ophthalmology resident capable of mitigating and treating such harms. The inconvenience of enrolling in the study will be mitigated by utilizing the wait time (10 to 40 minutes) during a routine clinic appointment. The conjunctival swab is a routine technique practiced by attending and resident ophthalmologists with minimal risk. Eye discomfort and pain during this procedure will be reduced with a soft cotton-tip applicator, and patients may be given routine topical anesthetics or eye lubricants after the procedure if needed. Topical anesthesia prior to swabbing and other methods of collecting microbiome samples such as eye irrigation will not be used due to their anticipated negative effect on sample quality.

8. Possible Benefits:

The participants will receive free FDA-approved treatment (artificial tears) for dry eye during the study and improved guidance on artificial tear choice after the study's conclusion based on the study results. This may not benefit all participants directly but may directly help some participants alleviate dry eye. There are no other direct benefits to participants.

To date, there is no data on whether this common artificial tear ingredient may have deleterious or favorable effects on the eye microbiome. The composition of eye microbiomes has been shown to have associations with eye diseases, including dry eye disease. This information may guide artificial tear choice in the future, as opposed to the status quo, where all brands of preservative-free artificial tears are treated as equivalent.

These benefits outweigh the minimal risk to enrolled study participants, who will be in the care of a trained ophthalmologist during the length of this study in the unlikely event that harm occurs to them. Our study methods use minimally invasive techniques to gather data and are routine in the setting in an ophthalmology clinic. We designed the study such that the risk of unreasonable harms such as billing for research time, eye infections, and patient discomfort are minimized or eliminated.

9. Conflict of Interest:

We do not have any conflicts of interest to disclose. Neither the principal investigator, co-investigators, or UF hold patents, licenses, or stock in the artificial tears used. We have no external sponsors.

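### Does handing over the study box before the baseline survey and swab compromise the baseline?

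*Combined protocol and SAP*

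**What the plan says.** Section 6 of the combined protocol and SAP (Research Plan, Initial Study Schedule) lists consent as step 4. Step 5 is "Staff gives a random box to the participant and attaches box label to informed consent form". Survey 1 is step 6, and step 7 is "Licensed staff collect 1st swab". The Assignment and Data Collection paragraphs agree: box and survey are given together, and the swab follows the survey.

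Under Before Study Enrollment, step 3 reads "Study staff assigns and labels cardboard boxes with numerical identifiers, then attaches spare labels" and step 4 reads "Principal investigator fills boxes with control or CMC artificial tears, consent copies, and patient instructions, then seals the boxes with tape". The Assignment paragraph describes "plain cardboard boxes with the identifier on removable adhesive labels". It gives the contents as follows: "Boxes will contain a copy of the informed consent form, participant instructions, and 21 plastic vials". The spreadsheet behind the boxes holds random "numerical identifiers keyed to either the control group receiving artificial tears without CMC or the treatment group receiving CMC artificial tears". The same paragraph states that patients are blinded to their group and that the study staff who hand out boxes, a group that excludes the principal investigator, do not know what is inside.

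**The concern.** A baseline should be taken before any exposure to study treatment. Swab 1 is the reference for the planned before/after diversity test (Sample Processing and Data Analysis), and survey 1 is the first reading of the symptom index. With the box handed over at step 5, a participant has 21 vials within reach while both are still outstanding.

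Several features of the text make this look worse:

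- No visible sentence tells the participant to keep the box closed until the swab.
- The participant instructions are packed inside the box, so they can be read only once it is open.
- Masking of the vials themselves is not described.
- The question on drop use is added only to survey 2, so use before swab 1 might not be recognisable in the data.

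A drop used before swab 1 would mean that the reference sample was no longer a pre-treatment sample. Separately, a person who leaves between steps 5 and 7 has been allocated but has no baseline.

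**Working it through.** No sample size, power or significance figure depends on the order of these steps, so the check is a comparison of the relevant text.

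**1. Is the order as described?** Yes. The step list runs consent, box, survey 1, swab 1, and the Assignment and Data Collection paragraphs give the same order. The text does not contradict itself.

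**2. What does the participant hold at step 5?** A plain, taped carton bearing a random number. The arm can be read from that number only with the spreadsheet. Holding the carton gives no exposure and no information about the arm. The figure of 21 vials describes what is in the carton, not what has reached the eye.

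**3. What has to happen for the baseline to be affected?** The participant must break the tape and use a vial, or open the carton and identify the product, during the clinic visit and before the swab. The protocol neither directs nor anticipates this. If every box stays sealed through step 7, exposure before swab 1 is nil and so is the bias.

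**4. Could participants have been told to wait?** Yes. Consent counselling takes place before the box is handed over (Recruitment; Initial Study Schedule, step 4). The consent form and the participant instructions are not reproduced in the document, so their content cannot be counted as missing from the plan.

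**5. Does drawing the box at step 5 have a purpose?** Yes. Survey 1 has a field for the identifier and the swab tube needs a label (Data Collection), so the number must be fixed before both. Only physical custody of the carton could be moved, not the allocation.

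**6. What about people who stop between steps 5 and 7?** The number allocated is not stated. Recruitment gives 80 identified and up to 20 expected to drop out, so I assume between 80 − 20 = 60 and 80 allocated. One such person is then 1/80 = 1.25% to 1/60 = 1.67% of those allocated. This is the share of a single person, not an estimate of how many stop, for which the document gives no basis. Holding the box back would not change it, because the arm-keyed number would still be drawn before survey 1. While neither the participant nor the handing-out staff know the arm, leaving at this point cannot depend on the arm, so it costs a participant and not validity.

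**7. Does undescribed vial masking make the order a problem?** No. Participants open the box after the visit whenever it is handed over. Whether the vials can be told apart is a separate question, which the order of steps 5 to 7 does not settle.

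**The case for a change.** The strongest case for changing the order is that the protocol is careful about the ocular surface elsewhere. Participant Criteria excludes people who used CMC tears within 1 week. Section 7 rules out topical anaesthetic before swabbing because of sample quality, and places lubricants for comfort after the procedure. Giving out lubricant drops before the swab sits oddly beside this. There is also time for early use: enrolment is fitted into a clinic wait of 10 to 40 minutes, the survey is done in a private room, and no visible step checks the tape before swab 1. Labels are removable and spares exist, so staff could use the number and keep the carton until after the swab at what looks like little cost. That would prevent early use physically, without relying on the participant.

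All of this stands as a description, and keeping the carton would be sensible housekeeping. It does not show a fault. An opportunity is not an exposure, and the tape, the uninformative number and the stated blinding already stand between the two. The anaesthetic rule concerns sample quality at any swab and is not a rule about baseline. The analysis text names only diversity tests, so no planned change-in-symptoms analysis depends on survey 1. Going further and withholding the box from anyone without a first swab, with that person logged as outside the comparison, would add a restriction on supply and an exclusion after allocation, neither of which the plan contains.

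**Conclusion.** The concern does not hold. The sequence is quoted correctly, but following it as written yields a pre-treatment, blinded baseline, and the bias is zero while boxes stay sealed. No other size can be derived from the document: it reports no early opening and gives no rate for it, and the 1.25% to 1.67% per person describes a loss that moving the handover would leave unchanged.

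This conclusion rests on the safeguards working as stated: tape intact until swab 1, box numbers that do not reveal the arm, and blinded participants and handing-out staff. It also takes into account that the consent text and participant instructions cannot be seen. When to hand over a sealed carton is a procedural preference, and no result of the trial can be shown to depend on it.

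### Participants are told the comparator may be a placebo, although the protocol itself describes the control as an approved standard therapy

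*Combined protocol and SAP*

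**What the plan says.** The Research Intervention bullet of section 6 defines two arms: CMC-free artificial tears as control and a commercial CMC product as treatment. It has participants "told that they may have received either CMC or a placebo". The next two sentences describe the products differently: "Both are FDA-approved for over-the-counter use and for treatment of dry eye", and "Both interventions are standard therapies for dry eye disease". The bullet closes by excluding people for whom artificial tears are not standard therapy.

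Section 8 (Possible Benefits) makes no distinction between arms: "The participants will receive free FDA-approved treatment (artificial tears) for dry eye during the study".

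On masking, the Assignment bullet says "Patients will be blinded to their assigned intervention group" and describes "plain cardboard boxes with the identifier on removable adhesive labels". On self-report, the Data Collection bullet says "Electronic surveys will contain the Ocular Surface Disease Index"; the survey is given at both visits, and the second adds one question on drop use. The aim in section 5 and the tests under Sample Processing and Data Analysis concern the microbiome only.

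**The concern.** A lay participant hears placebo as an inactive product. Here both products are approved for the condition and in standard use, so what participants are to be told about one of the two possible assignments is wrong. It is an instruction that the trial carries out with each person enrolled.

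Two things are at stake. The first is the accuracy of participant information, which matters without any statistical argument. The second is exposure and follow-up. The drops are self-administered from a box of 21 vials, and compliance rests on one self-reported question. Someone who thinks the drops may be inert has less reason to use them or to come back. Less use in the CMC arm means less exposure to the ingredient under study, and fewer returns mean fewer second swabs.

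**Working it through.** No arithmetic settles this point. It depends on no error rate, effect size, standard deviation or allocation ratio, and the plan states no figure to reproduce. The check sets the statements side by side.

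1. **What participants are told** (section 6, Research Intervention): CMC or a placebo.
2. **What the control is** (same bullet): CMC-free artificial tears, approved for dry eye and a standard therapy for it.
3. **What participants are said to receive** (section 8): approved treatment for dry eye, with no arm excepted.
4. **What the control is called elsewhere**: control, or artificial tears lacking CMC. The word placebo appears once, in the sentence about what participants are told.

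Statements 2 and 3 agree with each other. Statement 1 conflicts with both, so the description given to participants is the one out of line.

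**Does the wording bias the comparison between arms?** Every participant hears the same sentence, and participants are blinded. While the blind holds, belief cannot depend on arm. Any effect on symptom scores, reported drop use or return then acts as a common shift and does not by itself create a difference between CMC and control.

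**Does it reach the planned tests?** Those tests concern alpha and beta diversity from sequenced swabs. Expectation does not directly change a sequencing result. The Ocular Surface Disease Index is collected, but no outcome role or test is stated for it.

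**What indirect route remains?** If belief in a possible placebo lowers drop use in both arms, CMC exposure in the treatment arm falls. Any true effect of CMC on the microbiome would then tend to look smaller. If it lowers return, fewer before-and-after pairs are available. The Recruitment bullet refers to 80 patients and allows for up to 20 dropouts, which leaves 80 − 20 = 60 if all 80 enrol and all 20 are lost. The documents do not say how much of any loss might come from this wording, so the effect stays unquantified.

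**The case against.** The strongest defence is that placebo is shorthand for a product lacking the ingredient under test, and that the same bullet describes the control correctly for any professional reader. The title, too, calls the trial controlled and not placebo-controlled. This explains how the word may have got in, and it makes it unlikely that a careful reader of the protocol would mistake the design. It does not help participants: the sentence describes what they are told, and nothing says the word is explained to them.

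Three stronger readings are tempting, and the documents support none of them.

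- **That symptom scores are biased between arms, with an inflated false-positive rate.** This needs belief to differ by arm, so participants would have to identify their product. That is possible: the CMC product is commercial, and only a plain outer box is described, with nothing on relabelled or matched vials. It is not established, and it would be a masking fault separate from this sentence. Any error rate would also need an assumed shift and an assumed number per arm, for a comparison the plan does not contain.
- **That the wording drives the anticipated dropout or the anxiety listed in section 7.** Neither is linked to the word placebo. Eligible patients are already due back in 1 week, and blinded assignment could cause anxiety whatever the wording.
- **That the consent form is wrong.** Neither it nor the participant instructions are in the text available for this review. Only the protocol's account of what participants are told can be called inaccurate.

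**Conclusion.** The point holds as an inaccuracy in participant information. The protocol prescribes a statement about the comparator that its own description of the products contradicts, and it applies to everyone enrolled. It should be corrected, because it is an instruction to be carried out and the correction is nearly free.

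Its statistical weight is small. No bias in the contrast between CMC and control follows from the wording alone, and no planned test uses the symptom score. A plausible reduction in drop use or return in both arms remains, which would dilute exposure and cost paired samples. Its size cannot be estimated from the documents.

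This conclusion assumes that participants are told what the Research Intervention bullet says, that they take placebo in its ordinary sense, and that the blind holds.

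**What to change.** Replace the sentence in the Research Intervention bullet with: *told that they will receive one of two FDA-approved over-the-counter artificial tears, one containing CMC and one without CMC.* This uses the protocol's own account of the products, reveals nothing about assignment, and changes no treatment.

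Check that the consent form and the participant instructions in the box say the same, and amend them if they do not. In reports, describe the comparator as CMC-free artificial tears, an active control.

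The cost is a minor IRB wording amendment. There is no effect on sample size, assignment, blinding or analysis.

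### The only contrast the analysis names is before versus after treatment; no stated test compares CMC with control, so a change common to both arms could be read as a CMC effect

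*Combined protocol and SAP*

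**What the plan says.** The design is comparative. Section 4 (Background) states that "we are conducting a similar study on the use of artificial tears containing CMC compared to control artificial tears without CMC". Section 5 (Specific Aims) adds: "We aim to examine whether carboxymethylcellulose in artificial tears changes the eye microbiome and identify which bacterial genera are enriched". In section 6, the Assignment paragraph says "This study design will include an experimental control, random assignment, and double blinding of staff and participants", and the Data Collection paragraph sets the second sample: "Upon 1 week follow-up, participants will be swabbed again and complete a second survey".

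The inferential plan is a single sentence at the end of the Sample Processing and Data Analysis paragraph in section 6. For alpha diversity: "Differences in alpha diversity before and after treatment will be tested by PERMANOVA using the vegan R package". For beta diversity: "differences in beta diversity will be tested by ANOVA using the nlme R package". The only other analysis step with a possible grouping is descriptive: "microbiomes will be grouped by principal coordinate analysis using the phyloseq R package", with no grouping variable given. The abstract and the task list in section 6 name tools but no contrast.

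**The concern.** The aim concerns CMC, and randomisation was introduced to isolate it. A before/after contrast does not use the randomisation. Run on both arms pooled, it estimates the average change over a week of using some artificial tear. Run within the CMC arm, it estimates the CMC effect plus everything else that changed in that week.

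Those other influences are plausible here. The control is itself an eye drop, all participants are swabbed twice, and recent users of CMC tears are excluded, so some people in either arm may be starting a lubricant. A shift shared by the arms would then count as evidence about CMC.

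Running the test in each arm and concluding for CMC because one is significant and the other is not does not solve this. A difference in significance is not a test of the difference. Section 8 expects the results to guide the choice of artificial tears, so a misattributed change could influence practice.

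**Working it through.** **What the text specifies**

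| Analysis | Contrast named | Arm named as a factor? |
|---|---|---|
| Alpha diversity, PERMANOVA | Before versus after | No |
| Beta diversity, ANOVA in nlme | None | No |
| Principal coordinate analysis | None (descriptive) | No |
| Enriched genera (section 5) | None; no test stated | No |

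**Inputs for the illustration.** From the Recruitment paragraph of section 6: 80 patients, up to 20 dropouts, so 80 − 20 = 60 completers. The documents give no alpha, allocation ratio, standard deviation, pairing rule or size of common shift. Assumed: two-sided 5%, even split (30 per arm), normal changes, no CMC effect, and the same shift δ in both arms, in SD of the within-person change. The plan has no power figure to reproduce.

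**Paired before/after test.** The statistic is noncentral t with n − 1 degrees of freedom and noncentrality δ√n. For the CMC arm, n = 30 and the critical value is 2.045. At δ = 0.2 the noncentrality is 0.2 × √30 = 1.095 and the rejection probability is 0.185. At δ = 0.3 it is 1.643, giving 0.356. At δ = 0.5 it is 2.739, giving 0.754. Pooling both arms, n = 60 gives 0.332, 0.628 and 0.968.

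**CMC significant, control not.** With independent arms this is p(1 − p): 0.185 × 0.815 = 0.151; 0.356 × 0.644 = 0.229; 0.754 × 0.246 = 0.185. With no shift it is 0.05 × 0.95 = 0.0475.

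**Named test, pairing ignored.** The plan names PERMANOVA and states no permutation restriction. A permutation test on the Shannon index (Euclidean distance, free permutation, 3,000 simulated trials with 499 permutations each), with an assumed correlation r = 0.5 between a person's two swabs, gives the lower rows below.

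| Rejection rate with no CMC effect | δ = 0.2 | δ = 0.3 | δ = 0.5 |
|---|---|---|---|
| CMC arm, paired | 19% | 36% | 75% |
| Pooled arms, paired | 33% | 63% | 97% |
| CMC significant, control not, paired | 15% | 23% | 19% |
| CMC arm, free permutation, r = 0.5 | 5% | 13% | 46% |
| Pooled arms, free permutation, r = 0.5 | 11% | 32% | 85% |
| CMC significant, control not, free permutation, r = 0.5 | 5% | 11% | 24% |
| Between-arm test of change | about 5% | about 5% | about 5% |

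The free-permutation rates depend on r. With an unpaired t-test as a proxy, the CMC-arm rate at δ = 0.2 runs from 19% at r = 0 to 1% at r = 0.7. At δ = 0.5 it runs from 77% to 20%.

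**Without dropout** (40 per arm, paired), the CMC-arm rates are 23%, 46% and 87%.

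**The case against.** The strongest reply is that this is under-specification, not a wrong analysis. The intent to compare with control is explicit in sections 4 and 6, every identifier is keyed to an arm, and nlme fits mixed models that could carry arm, visit and their interaction. Harm arises only if the investigators disregard their own control group, which the plan does not say they will do.

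That is fair as far as it goes: an arm comparison is neither stated nor ruled out. But the document serves as the statistical plan, and the one contrast it writes is not the one the aim needs. Its meaning is also unclear. The Research Intervention paragraph attaches the word treatment to the CMC product alone, so the contrast could mean the CMC arm only, each arm separately, or both pooled. The analyst could choose among these after seeing the data. Adding arm to the beta-diversity model would not repair the alpha-diversity test.

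It is also true that the rates rest on an assumed shift and, where pairing is ignored, on an undocumented correlation; at r = 0.5 and δ = 0.2 the CMC-arm rate does not exceed 5%. A pooled rejection is an error only if it is attributed to CMC. These points limit the illustration. They do not supply the missing contrast.

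The same sentence also appears to exchange the methods for alpha and beta diversity. That is a separate matter, and swapping them back would still leave no arm comparison.

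**Conclusion.** The concern holds. No test in the plan is stated to use the randomised arm, and the before/after contrast, pooled or arm by arm, cannot answer whether CMC changes the eye microbiome. This follows from the text and needs no numerical assumption.

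How often a false CMC claim would result cannot be fixed from the documents, because it depends on the size of any common shift and on how pairing is handled. Under the stated assumptions, the CMC-arm test rejects between 19% and 75% of the time when pairing is respected. It can fall below 5% when pairing is ignored and the swabs are strongly correlated. Only the between-arm test holds its 5% level whatever the common shift. The matter should be settled before the data are analysed by arm.

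**What to change.** State the primary alpha-diversity analysis as the CMC-minus-control difference in week-1 Shannon index adjusted for baseline Shannon index, with a 95% confidence interval and participants analysed as randomised. The arm-by-visit term of an nlme mixed model with participant as random effect is an acceptable alternative. For composition, test the arm-by-visit effect using both visits, permuting arm labels across whole participants so that each person's two samples stay together. Report within-arm changes as descriptive only.

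A plain between-arm test of change would also remove the bias, so baseline adjustment is a gain in precision only. With 30 per arm and 80% power, the detectable difference at week 1 is 0.736 SD of the Shannon index. Multiply by √(2(1 − r)) for change scores and by √(1 − r²) with adjustment: 0.87 against 0.70 at r = 0.3, 0.74 against 0.64 at r = 0.5, and 0.57 against 0.53 at r = 0.7.

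The cost is wording in the analysis section. Arm, baseline swab and week-1 swab are already to be collected.
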